#### Central lab collection and processing:

PK, P50, and erythropoetin labs will be collected, processed, and stored as described in Study Lab Manual.

**Voxelotor administration**: The day after obtaining written, informed consent, 500 mg of voxelotor will be administered two times a day (for a total daily dose of 1000 mg per day) for 5 days. This dose may increase to a total maximum daily dose of 1500 mg (500 mg three times a day) if subject tolerates initial dose as determined by Principal Investigator (PI). Subjects will be dosed orally with approved tablets or recently approved dispersible tablet in water and given via feeding tube (when indicated). In the event the voxelotor administration needs to be modified during one of the study administration days for patient safety reasons, the PI will follow the dose modification guidelines for study related adverse events (Table 4). If the PI determines discontinuation of voxeletor is necessary for patient safety, then the protocol will progress to the wash out phase identified in the Schedule of Activities table 2.

If a patient on the lung transplant list receives an "initiation call" from the lung transplant coordinators, study medication will be held until a determination is made to proceed with solid organ transplantation. In the event the study patient does not receive the solid organ transplant, study medication administration will be resumed as previously scheduled and missed doses will be not be considered protocol deviations as the PK and pharmacodynamics (PD) of Voxelotor in the setting of surgery, blood loss, and blood transfusion is unknown. In the event the study patient receives a "go call" for solid organ lung transplant then study medication will be discontinued and the subject will proceed to the study wash out phase.

Voxelotor is oral administration only and the effect of blood transfusion "diluting" the Voxelotor modified RBCs is unknown, so the effect of Voxelotor in this setting will be confounded by the common scenario of blood transfusion and/or hemodilution and they will enter the wash-out period. Also, the indication for Voxelotor, to maintain SaO2 in the face of a significant Alveolar-arterial pO2 gradient, will have passed with the implantation of donor lungs.

Study completion is at the end of 2 day wash out period defined by 2 days after the last administration of Voxelotor.

Physiological measures and laboratory data to be recorded from electronic medical record (EMR) are detailed on the Schedule of Activities Table 2.

Table 2: Schedule of Activities and/or other clinical outcomes

Table 2. Schedule of F	Bas	eline rements	Dosing Period				Wash out Period		
Study Day	D-2	D-1	D1	D2	D3	D4	D5	D6	D 7
Screening	X								
Consent	X								
Voxelotor Dosing			X	X	X	X	X		
Physiological									
ESLD and ALI cohort (At rest and with exercise*)									
$SpO_2$	X	X	X	X	X	X	X	X	X
FiO 2	X	X	X	X	X	X	X	X	X
S/F ratio calculation	X	X	X	X	X	X	X	X	X
HR	X	X	X	X	X	X	X	X	X
ALI cohort									
paO 2	X	X	X	X	X	X	X	X	X
SaO 2	X	X	X	X	X	X	X	X	X
P/F ratio calculation	X	X	X	X	X	X	X	X	X
paCO 2	X	X	X	X	X	X	X	X	X
A-a gradient calculation	X	X	X	X	X	X	X	X	X
Borg Dyspnea Scale rating	X	X	X	X	Х	X	Х	X	X
Laboratory									
Erythropoietin (5ml)		X		X				X	
PK (2ml)		X	X	X	X	X	X	X	X
P50 (3ml)		X	X	Х	X	X	X	X	X
BMP (4.5ml)			X	X	X	X	X	X	
CMP (4.5ml)		X							X
CBC (3ml)		X	X	X	X	X	X	X	X
Pregnancy test (2 ml)		X							
Con meds	X	X	X	X	X	X	X	X	X
Adverse Events			X	X	X	X	X	X	X

\*only if feasible, ambulatory patients only. Exercise protocol is SOC and data collected will be reviewed from medical record.

\*\*

## 3.2 Primary Study Endpoints

The primary outcome will be change in S/F ratio from baseline to 2 days after initiation of Voxelotor treatment.

## 3.3 Secondary Study Endpoints

Secondary study endpoint is change in S/F ratio from baseline to 5 days after initiation of Voxelotor treatment.

Exploratory endpoints: Pre and post Voxelotor use compare

- ° FiO2 requirements
- ° Oxygen delivery modality
- Combined end-point of de-escalation of FiO2 and/or oxygen delivery modality
- Nadir SpO2
- Oxygen flow
- healthcare utilization
- Dyspnea scale

## 3.4 Primary Safety Endpoints

Based on current knowledge of safety profiles, a primary safety end-point will not be specified. Safety will be assessed by tracking SOC clinical laboratory tests (hematology profile, serum chemistry, erythropoietin and urinalysis), physical examinations, vital signs, 12-lead electrocardiogram (ECG) pre-administration and after Day 5. Hematology and chemistry labs will be screened before study drug administration and repeated daily until end of study. Vital signs will be monitored during study drug administration. Adverse events (AEs) and concomitant medications will be monitored and documented throughout the study. Of note, in a recent study in patients with impaired renal function, there was no deterioration of renal function. https://www.ncbi.nlm.nih.gov/pmc/articles/PMC7984382/

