#### 4.2 Exclusion Criteria

- 1. Minors (<18 years)
- 2. Pre-existing congestive cardiac failure (NYHA III or IV)
- 3. Medically significant, non-revascularized coronary artery disease
- 4. Inability to obtain informed consent from LAR
- 5. Pregnancy
- 6. Incarcerated individual.
- 7. Failure of another vital organ.
- 8. Severe hepatic impairment (Childs-Pugh C) or liver enzymes > 4x upper limit of normal (ULN) at screening.
- 9. Unstable acute kidney injury/rising creatinine.
- 10. Chronic neuromuscular disease requiring mechanical ventilation
- 11. Not anticipated to survive >48 hours
- 12. Limited therapeutic goals (do not resuscitate, etc.)
- 13. History of Pulmonary Embolism (PE)
- 14. Requires treatment with Fluconazole or other moderate and strong CYP3A4 inhibitors listed in section 5.6
- 15. A patient with active bleeding complications requiring more than 1 unit of blood transfusion per day.
- 16. Participated in another clinical trial of an investigational drug (or medical device) within 30 days or 5-half-lives, whichever is longer, prior to consent, or is currently participating in another trial of an investigational or marketed drug (or medical device)
- 17. Any condition including the presence of laboratory abnormalities, which places the subject at unacceptable risk if he/she were to participate in the study
- 18. Any condition or concomitant medication that confounds the ability to interpret data from the study or safely use Voxelotor.

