### Adverse Event Reporting Period

The study period during which adverse events must be reported is normally defined as the period from the initiation of any study procedures to the end of the study treatment follow-up. For this study, subjects will be followed for AEs from the time of voxelotor administration until 2 days after the last administration of voxelotor as defined by the wash out period.

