#### Abnormal Laboratory Values

A clinical laboratory abnormality should be documented as an adverse event if any one of the following conditions is met:

- The laboratory abnormality is not otherwise refuted by a repeat test to confirm the abnormality
- The abnormality suggests a disease and/or organ toxicity
- The abnormality is of a degree that requires active management; e.g. change of dose, discontinuation of the drug, more frequent follow-up assessments, further diagnostic investigation, etc.

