## 8.2 Recording of Adverse Events

At each contact with the subject, the investigator must seek information on adverse events by specific questioning and, as appropriate, by examination. Information on all adverse events should be recorded immediately in the source document of the case report form (CRF). All clearly related signs, symptoms, and abnormal diagnostic procedures results should be recorded in the source document, though should be grouped under one diagnosis.

All adverse events occurring during the study period must be recorded. The clinical course of each event should be followed until resolution, stabilization, or until it has been determined that the study treatment or participation is not the cause. Serious adverse events that are still ongoing at the end of the study period must be followed up to determine the final outcome. Any serious adverse event that occurs after the study period and is considered to be possibly related to the study treatment or study participation should be recorded and reported immediately.

Requirements for reporting of an AE to various entities (IRB, FDA, and Sponsor) differ according to whether or not the AE represents an unanticipated problem. This study will follow 21 CFR 312.32 IND Safety Reporting guidelines and DUHS prompt reporting to the IRB policy for events that occur with this study.

Subjects in this study will be followed for AEs from the time of voxelotor administration until 2 days after the administration of voxelotor as defined by study wash out period. The PI will be responsible for ensuring participants' safety.

[name] will be the physician responsible for reviewing and evaluating all adverse events. [name] will evaluate the safety of voxelotor treatment in all subjects by following adverse events and assigning likelihood of causality. Related AEs will be reported to IRB. Nonrelated AEs will be tracked by the study team.

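### Chemistry is scheduled every day, but on the usual panel contents liver enzymes are scheduled on none of the five dosing days, and Section 3.4 does not say so

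*Combined protocol and SAP*

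**What the plan says.** Section 3.4 sets no primary safety endpoint and describes safety follow-up in general terms. On laboratory tests it says: "Hematology and chemistry labs will be screened before study drug administration and repeated daily until end of study". Neither the panel nor the analytes are named.

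The detail is in Table 2 (Section 3.1) and the visit lists in Sections 6.2 to 6.7, which agree with each other. The CMP is drawn on the day before dosing and on Day 7. The BMP is drawn on Days 1 to 6. Both are listed at 4.5 mL. The documents do not state what either panel contains.

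Dosing covers Days 1 to 5: "500 mg of voxelotor will be administered two times a day (for a total daily dose of 1000 mg per day) for 5 days". Days 6 and 7 are wash-out.

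Liver enzymes are named explicitly in one place, exclusion criterion 8 in Section 4.2: "Severe hepatic impairment (Childs-Pugh C) or liver enzymes > 4x upper limit of normal (ULN) at screening". In Section 8.1, under Abnormal Laboratory Values, one of the conditions that makes a laboratory abnormality an adverse event is: "The abnormality suggests a disease and/or organ toxicity". The safety analysis in Section 7.2 is a tabulation of the adverse events observed.

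**The concern.** Someone who reads Section 3.4 alone would expect the chemistry measured before dosing to be the chemistry measured each day afterwards. The schedule does not work that way: the pre-dose panel is a CMP, and the next CMP is on the last study day.

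On the usual panel contents, renal values and electrolytes are followed daily while liver enzymes are not scheduled during treatment at all. Three uses of the data are affected:

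- The adverse-event tabulation could show no hepatic laboratory events during dosing simply because no liver value was scheduled then.
- Sections 4.4.1 and 8.4 enrol the first five participants one at a time so that each can have a full safety review. That review would hold no scheduled on-treatment liver value.
- The trial is a pilot for a later study. A planner could take an empty hepatic row as reassurance that the data cannot give.

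**Working it through.** **Plan's own figure.** The documents give no figure for liver-test coverage, so there is none to reproduce. The check is a count of scheduled days.

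**Inputs** (Table 2, with the chemistry rows checked against Sections 6.2 to 6.7):

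| Day | D-2 | D-1 | D1 | D2 | D3 | D4 | D5 | D6 | D7 |
|---|---|---|---|---|---|---|---|---|---|
| Phase | Baseline | Baseline | Dosing | Dosing | Dosing | Dosing | Dosing | Wash-out | Wash-out |
| CMP | – | X | – | – | – | – | – | – | X |
| BMP | – | – | X | X | X | X | X | X | – |
| CBC | – | X | X | X | X | X | X | X | X |

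No blood test is scheduled on D-2, so the denominator for every count is the 8 laboratory days from D-1 to D7.

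**Assumption.** A CMP includes liver enzymes and a BMP does not. This is the usual meaning of the panels and is not stated in the documents.

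**Counts.**

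- Any chemistry panel: 2 CMP days + 6 BMP days = 8 of 8.
- CBC: 8 of 8.
- Liver enzymes (CMP): 2 of 8.
- Liver enzymes on dosing days: 0 of 5.
- Liver enzymes on wash-out days: 1 of 2 (D7; D6 is a BMP).
- Consecutive laboratory days without a scheduled liver enzyme: D1 to D6 = 6.

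**If the assumption is wrong.** If the site's BMP includes liver enzymes, coverage is 8 of 8 and 5 of 5. The gap disappears, and what remains is that the documents should say so.

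**Blood volume if a CMP replaced each BMP.** 6 × (4.5 − 4.5) = 0 mL per patient.

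**Number of panels affected.** 6 days × 20 patients = 120 at most.

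**Side check on volume.** The Table 2 draws sum to 3×5 (erythropoietin) + 8×2 (PK) + 8×3 (P50) + 6×4.5 (BMP) + 2×4.5 (CMP) + 8×3 (CBC) + 1×2 (pregnancy test) = 15 + 16 + 24 + 27 + 9 + 24 + 2 = 117 mL. Section 3.1 states 109 mL. That mismatch is a separate matter and does not affect this point, because changing the panel leaves the sum at 117 mL.

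**The case against.** The strongest objection is that nothing in the plan is contradicted. A reader might infer that Section 3.4 promises one thing and Table 2 delivers another. A BMP is a chemistry panel, however, and a chemistry panel is scheduled on every laboratory day, so Section 3.4 is met literally. This stands: the fault is that Section 3.4 is unspecific, not that it is false.

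A reader might also infer that a hepatic event could come to light only in wash-out. The documents do not support that:

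- Section 3.4 says: "Safety will be assessed by tracking SOC clinical laboratory tests". It adds physical examinations, and: "Adverse events (AEs) and concomitant medications will be monitored and documented throughout the study".
- Section 8.2 requires: "At each contact with the subject, the investigator must seek information on adverse events by specific questioning and, as appropriate, by examination".
- The reporting period in Section 8.1 covers dosing: "subjects will be followed for AEs from the time of voxelotor administration until 2 days after the last administration of voxelotor".
- Patients are inpatients, and Section 3.1 takes laboratory data from the medical record.
- A patient who stops early moves to the wash-out schedule sooner.

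A symptomatic event, or one caught by routine testing, can therefore be recorded during dosing. The documents do not say how often liver tests are ordered as standard of care in these patients, or why. It cannot be assumed either that routine testing fills the gap or that it is ordered only on suspicion.

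Nor does the gap disable the dose-modification guidance in Table 4. That table acts on the grade of any event judged drug-related, whatever its source.

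Finally, the schedule has a rationale. Sections 1.5 and 4.4.1 single out renal function as a marker of tissue oxygenation, and the side effects listed in Section 1.5 include no hepatic event. Exclusion 8 limits entry and does not commit the trial to liver monitoring on treatment. Liver tests before and after a five-day course are a defensible choice. This is a good reason for low severity, but it does not remove the need to say what daily chemistry covers.

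**Conclusion.** The point holds in a limited form. On the usual panel contents, liver enzymes are protocol-scheduled on 2 of 8 laboratory days and 0 of 5 dosing days, while Section 3.4 lets a reader suppose that the pre-dose chemistry is repeated daily. A silent rise between D-1 and D7 has no scheduled detection, and one that resolves by D7 would be seen only if standard-of-care testing or clinical review picked it up.

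The conclusion rests on one assumption from outside the documents, the panel contents. The day counts come directly from Table 2 and Section 6. The point does not touch the primary or secondary outcome, the documents report no hepatic signal, and other routes of detection exist. Severity is low. It is worth raising because the correction costs little and decides whether an empty on-treatment hepatic row can be interpreted.

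**What to change.** Reconcile Section 3.4 with Table 2 and Sections 6.3 to 6.6, and name the panel. The preferred form is to repeat the panel used as the pre-dose reference on the existing 4.5 mL draws on D1 to D6, so that each on-treatment value has a matching baseline. This needs edits to Table 2 and four visit lists. It adds 0 mL of blood and no visit or staff time. The downside is the assay cost difference for up to 120 panels.

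If the BMP is kept, state in Section 3.4 that daily chemistry excludes liver enzymes. State in the adverse-event report that hepatic values were protocol-scheduled only at D-1 and D7, so an absence of on-treatment hepatic laboratory events is not evidence that there were none. This costs one sentence in each place, and the gap remains.

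In either case, define CMP and BMP in the abbreviations or the laboratory section.

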# 4 Subject Selection and Withdrawal

#### 4.1 Inclusion Criteria

- 1. Oxygen dependency due to an end-stage lung disease (pre-lung transplant population) or ALI/acute lung injury (for example but not limited to primary allograft dysfunction, infectious pneumonia, aspiration, non-cardiogenic pulmonary edema). ALI will be defined as per Berlin criteria with a P/F ratio < 100 denoting severe acute respiratory distress syndrome (ARDS), < 200 denoting moderate and < 300 mild ARDS. ALI and mild ARDS are considered synonymous. In the event of inability to obtain arterial blood gas analysis to calculate a P/F ratio, we will consider a range of patients requiring standard nasal cannulae flowing at 6 LPM (liters per minute) to maintain SaO2 > 90% as ALI, and Salter High -Flow nasal cannulae at 12-15 LPM in order to maintain SaO2 > 85% as severe ARDS.
- 2. At least 48 hours of stable, increased oxygen requirement or ventilatory support prior to the start of drug administration if consented.

#### 4.2 Exclusion Criteria

- 1. Minors (<18 years)
- 2. Pre-existing congestive cardiac failure (NYHA III or IV)
- 3. Medically significant, non-revascularized coronary artery disease
- 4. Inability to obtain informed consent from LAR
- 5. Pregnancy
- 6. Incarcerated individual.
- 7. Failure of another vital organ.
- 8. Severe hepatic impairment (Childs-Pugh C) or liver enzymes > 4x upper limit of normal (ULN) at screening.
- 9. Unstable acute kidney injury/rising creatinine.
- 10. Chronic neuromuscular disease requiring mechanical ventilation
- 11. Not anticipated to survive >48 hours
- 12. Limited therapeutic goals (do not resuscitate, etc.)
- 13. History of Pulmonary Embolism (PE)
- 14. Requires treatment with Fluconazole or other moderate and strong CYP3A4 inhibitors listed in section 5.6
- 15. A patient with active bleeding complications requiring more than 1 unit of blood transfusion per day.
- 16. Participated in another clinical trial of an investigational drug (or medical device) within 30 days or 5-half-lives, whichever is longer, prior to consent, or is currently participating in another trial of an investigational or marketed drug (or medical device)
- 17. Any condition including the presence of laboratory abnormalities, which places the subject at unacceptable risk if he/she were to participate in the study
- 18. Any condition or concomitant medication that confounds the ability to interpret data from the study or safely use Voxelotor.

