# 3 Study Design

## 3.1 General Design

Following a screening period and observation that clinical status is stable and requiring substantial oxygen support for 48 hours, subjects with decompensation of ESLD or ALI with hypoxemia, will be approached for informed consent. The nature of the risks and benefits associated with participation in the study will be explained to all potential study subjects or legally authorized representative (LAR). Written informed consent must be obtained before the subject can begin any screening procedures that are not considered standard patient care.

**Physiological data:** Physiological data at screening, baseline, study day 1-5, and up to two days post voxelotor administration will be recorded from standard of care with the only exception being SpO2/FiO2 (S/F) ratio measurements, which will be obtained at the same intervals but by the qualified and delegated study staff or medical team through the use of an FiO2 weaning maneuver.

Physiological measures to be recorded are detailed on the Schedule of Activities table 2.

**FiO2** Weaning Maneuver: The process of titrating FiO2 down slowly until the study patient's SpO2 measurement is approximately 88%. This will provide the study team with values for an S/F ratio that more closely represents the transition to the steepest part of the oxygen dissociation curve (ODC). Measurements that represent this transition on the ODC will allow for more precise comparison and provide more accurate trending data. Once completed, the oxygen delivery system will be titrated back to achieve SpO2 goals prescribed by the medical team.

**Modified Borg Dyspnea Scale:** Study subjects will be asked to rate their dyspnea symptoms daily to record their perceived shortness of breath.

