## 4.4 Early Withdrawal of Subjects

### 4.4.1 When and How to Withdraw Subjects.

Study completion is at the end of 2 day wash out period defined by 2 days after the last administration of Voxelotor. If a patient withdraws informed consent, the patient will be withdrawn from Voxelotor study treatments and all study related assessments.

A patient will be withdrawn from the study treatment if any of the events listed below occur but should continue to be followed according to the intervention table:

- Decision by the Investigator that it is not in the best interest of a patient to continue treatment.
- Subjects are free to withdraw their consent at any time; the PI will withdraw a subject if any adverse response is thought to be due to Voxelotor.
- If a patient receives a "go call" for solid organ lung transplant then study medication will be discontinued and the subject will proceed to the study wash out phase, as the PK and PD of Voxelotor in the setting of surgery, blood loss, and blood transfusion is unknown. Voxelotor is oral administration only and the effect of blood transfusion "diluting" the Voxelotor modified RBCs is unknown, so the effect of Voxelotor in this setting will be confounded by the common scenario of blood transfusion and/or hemodilution. Also, the indication for Voxelotor, to maintain SaO2 in the face of a significant Alveolar-arterial pO2 gradient, will have passed with the implantation of donor lungs.
- If a patient suffers bleeding complications requiring blood transfusion, as the PK and PD of Voxelotor in the setting of blood loss and blood transfusion is unknown. The effect of blood transfusion "diluting" the Voxelotor modified RBCs is unknown, so the effect of Voxelotor in this setting will be confounded and they will enter the wash-out period.
- As Voxelotor increases the binding of oxygen to hemoglobin (providing the treatment effect of increased SpO2 for a given pO2), we will monitor for the possibility of inadequate oxygen being off-loaded to the tissues by tracking venous blood gases for evidence of metabolic acidosis from tissue beds and tracking renal function as a reflection of adequacy of tissue oxygen during administration of Voxelotor.

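### Exclusion 15 admits active bleeding transfused at up to 1 unit a day, but Section 4.4.1 stops treatment for any bleeding complication that needs transfusion

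*Combined protocol and SAP*

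**What the plan says.** **Entry.** Section 4.2, exclusion 15, excludes "A patient with active bleeding complications requiring more than 1 unit of blood transfusion per day". Bleeding that needs 1 unit a day or less is not excluded by this criterion.

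**Withdrawal.** Section 4.4.1 opens its list with "A patient will be withdrawn from the study treatment if any of the events listed below occur", adding "but should continue to be followed according to the intervention table". One listed event begins "If a patient suffers bleeding complications requiring blood transfusion, as the PK and PD of Voxelotor in the setting of blood loss". The bullet goes on to say that the diluting effect of transfusion on voxelotor-modified red cells is unknown, "so the effect of Voxelotor in this setting will be confounded and they will enter the wash-out period". It gives no number of units, no daily rate and no exemption for bleeding already present when the patient was enrolled.

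**Transplant setting.** The voxelotor administration paragraph in Section 3.1 gives the same dilution reason for patients who go to transplant: the effect "will be confounded by the common scenario of blood transfusion and/or hemodilution and they will enter the wash-out period". It too has no unit threshold.

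**Endpoint and populations.** The primary endpoint is the change in S/F ratio from baseline to 2 days after the start of treatment (Section 3.2). The primary analysis population is the protocol-compliant one, which requires the drug exposure that the protocol calls for; an all-treated population is secondary (Section 7.3).

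**The concern.** Entry and withdrawal use different limits for the same kind of event. The entry rule tolerates some transfused bleeding, and the stopping rule tolerates none. A patient can therefore be enrolled in a state that, if it merely continues, requires treatment to stop.

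What is at stake is the usefulness of that patient's data. Treatment may stop before the primary time point, so the Day 2 S/F value may be off drug and taken after a transfusion. The patient may also not count as protocol-compliant. In a 20-subject pilot meant to supply an effect size for a later study (Section 7.1), it is worth avoiding the enrolment of someone who is likely to be stopped on a known criterion.

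**Working it through.** The plan gives no figure to reproduce. The check is a comparison of the two rules, followed by simple counts.

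**1. The rules side by side**

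| | Exclusion 15 | Section 4.4.1 bleeding bullet |
|---|---|---|
| Applied | at entry | after dosing starts |
| Trigger | active bleeding, more than 1 unit per day | bleeding complication needing transfusion |
| Unit threshold | more than 1 per day | none |
| Exemption for bleeding at entry | not applicable | none |
| Force | exclusion | mandatory stop of treatment |

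**2. One patient through both rules.** Take a patient with active bleeding who receives exactly 1 unit a day. At entry, 1 is not more than 1, so exclusion 15 does not apply. If the same need continues, the first transfusion for bleeding after the first dose meets the 4.4.1 trigger. If the bleeding stops before dosing, the trigger is not met.

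**3. Does anything reconcile them?** Inclusion 2 concerns stable oxygen or ventilatory need, not bleeding. Section 4.3 asks more broadly for a stable clinical status over 48 hours. Exclusion 17 (unacceptable risk) and exclusion 18 (conditions that confound interpretation) are general and do not name bleeding or transfusion. None of these sets a common threshold.

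**4. How much drug before the stop.** The starting regimen is "500 mg of voxelotor will be administered two times a day (for a total daily dose of 1000 mg per day) for 5 days", so 2 × 5 = 10 doses.
- Stopped on Day 1: at most 2/10 = 20%.
- Stopped on Day 2: at most 4/10 = 40%.
- At three doses a day throughout, 3 × 5 = 15 doses, and the shares are the same: 3/15 = 20% and 6/15 = 40%.

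These are upper bounds from the schedule, not estimates of impact.

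**5. Share of the sample.** Each case is 1/20 = 5% of planned subjects. The documents give no bleeding or transfusion rate, so the number of cases cannot be estimated. Its lower bound is 0.

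**The case against.** The best counter-argument is that 4.4.1 lists events that occur on treatment and speaks of a patient who suffers a complication, whereas exclusion 15 describes a state at entry. Read that way, bleeding already accepted at entry is not a new event and the rules do not collide. This reading is arguable, but the text does not limit the bullet to new bleeding. The dilution reason covers any transfusion after dosing starts, whenever the bleeding began. Under the new-events reading, a patient with fresh bleeding given 1 unit would be stopped while one already receiving 1 unit a day would stay on drug, with the same confounding.

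A second argument is that exclusion 18 already removes these patients. It may remove some. Used to remove all of them, it would leave the explicit 1-unit allowance with no function.

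Other objections stand, and they limit the point:
- The rules are not logically contradictory. Site staff can apply one at screening and the other after dosing; the result is inefficiency and ambiguity.
- The affected group is narrow: bleeding at entry, transfused at 1 unit a day or less, clinically stable for 48 hours, past exclusions 17 and 18, and still needing blood after the first dose.
- Section 7.3 does not define the required exposure, so loss from the primary population is possible, not certain. A patient stopped late on Day 2 could still give a Day 2 value that is partly on treatment.

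A reader might also infer two stronger things that the documents do not support. One is that the dilution reason applies equally to transfusion at entry. It does not, because no voxelotor-modified red cells exist before the first dose. The other is that these patients bear a special burden from the FiO2 weaning maneuver, in which SpO2 "measurement is approximately 88%. This will provide the study team with values for an S/F ratio". Every subject undergoes that maneuver, including at baseline, so it is not a harm of this mismatch.

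**Conclusion.** The mismatch is real and of low severity. As written, the plan can enrol and dose a patient who then meets a mandatory stopping rule at the first on-study transfusion for bleeding, possibly before the Day 2 primary measurement, and who may fall outside the protocol-compliant population.

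This rests on two conditions: that the 4.4.1 bullet is not confined to new bleeding, and that the patient's bleeding-related transfusion need continues after dosing begins. It would be wrong to infer that such patients are lost to the study. Follow-up continues after treatment stops, the all-treated analysis would include them, and the mixed model in Section 7.2 is specified for all S/F values. No claim about the size of bias or the probability of early withdrawal can be made from the documents.

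**What to change.** Reword exclusion 15 to read: *Active bleeding complications requiring blood transfusion*. Drop the unit threshold, and check the criterion at screening and again just before the first dose. Entry then matches the 4.4.1 trigger.

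Adding the 1-unit threshold to 4.4.1 would also align the rules. It would, however, keep on treatment patients whose effect the plan itself regards as confounded, so tightening entry fits the plan's reasoning better.

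The cost is a one-line amendment. A few candidates become ineligible or must wait until the bleeding has resolved.
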